4.3.2 RNA-Seq and Microarray Analysis of RNA

4.3.2.1 RNA-Seq Analysis

For RNA-Seq assays we will use Illumina's TruSeq RNA Access Library Prep Kit to generate RNA libraries. This reagent kit, which focuses on transcriptome coding regions, can be performed with as little as 20ng of degraded total RNA isolated from FFPE specimens. RNA libraries will be multiplexed and, following cluster generation, sequenced with 100 basepair (bp) single end (SE) reads to a depth of approximately 45 million reads per sample on an Illumina HiSeq2000 instrument. To mitigate assay noise we will perform RNA-Seq on each PEL RNA sample in triplicate, using an independently generated library for each RNA-Seq assay. Each sample will be barcoded and sequenced as part of a single pool with up to 30 samples loaded onto an 8-lane flow cell.

The general approach to RNA-Seq data analyses is as follows: Multiplexed RNA-Seq data will be deconvoluted to separate each of the samples, after which, sequencing adapters and poly-A/T tails will be trimmed using cutadapt software. Sequencing reads of length less than 20 base pairs will be removed. Reads will be aligned to the human genome using STAR software. Aligned reads will be realigned using GATK's IndelRealigner. Gene Expression: STAR genomic alignments will be filtered to remove any reads that align outside of Gencode exons. Remaining reads will be realigned to the Gencode transcriptome using bowtie2 and transcriptome alignments passed to eXpress for expression estimation. Gene expression will be calculated by summing the FPKM estimates for each of the gene's transcripts. Genes with expression greater than zero FPKM will be considered expressed. All of the RNA-Seq data that pass these quality metrics will then be normalized and then subjected to supervised analysis to identify genes differentially expressed between PEL treatment responders vs non-responders. This supervised analysis will be performed by means of t-test with multi-testing correction (Westfall & Young Permutation method)¹¹ (p < 0.05, FDR < 0.05). Based on past experience¹⁰, we expect that fewer than 500 genes will be found to be differentially expressed between treatment responders and non-responders. Lastly, we will take advantage of bioinformatic approaches to examine genes that are found to be differentially expressed between the sample groups. software. Bioinformatic such as Ingenuity Pathways (http://www.ingenuity.com), focus on the analysis of genetic networks and pathways and help place such genes, which may have prognostic significance, into biologic context.

Following quantification and quality assessment of the RNA, RNA-Seq analyses, as described above will be performed on 20 PEL specimens, 10 of which are from long-term survivors and 10 from non-long-term survivors. The resulting data will be assessed for quality and adequacy: the total number of reads compatible with a transcript on the RNA-Seq assay.

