1.1 Hypothesis

We hypothesize that there will be a sub-set of PEL clinical characteristics and differentially expressed genes in PEL cells that will be predictive of long-term survival (≥ 2 years), when data from long-term and short-term survivors of the disease are compared.

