1.2 Primary Objectives

1.1.1 Primary clinical objective:

Identify baseline clinical characteristics and treatment strategies in patients with AIDS-associated primary effusion lymphoma (PEL) that correlate with long-term survival (≥ 2 years).

1.1.2 Primary genomic objective:

Identify differentially expressed genes in PEL that are associated with long-term survival (≥ 2 years).

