An initial genomic evaluation of 9 PEL cases was published by Klein et al., in 2003 and reported PEL as having a distinct profile from other NHLs – including those from immunocompetent and HIV-seropositive hosts – with features of both immunoblasts and plasma cells⁷. Although distinct, AIDS-PEL had a profile most similar to EBV+ immunoblastic diffuse large B cell lymphoma. Despite the limited sample size, they were able to identify 51 genes differentially expressed between PEL cells and normal B cells as well as NHL, including AIDS-NHL.

Past work on gene expression profiling of AIDS-PEL determined that it was quite different from other types of non-HIV and AIDS-related non-Hodgkin's lymphoma⁷ and discerned sub-types of PEL that were primarily associated with the presence, or absence of either KSHV or EBV⁸. In the first study, 9 cases of fresh AIDS-PEL specimens, in the form of cell blocks prepared from cytospins of the PEL fluid, were expression profiled on the Affymetrix U95 GeneChip. Although distinct, AIDS-PEL had a profile most similar to

EBV+ immunoblastic diffuse large B cell lymphoma. Despite the limited sample size, they were able to identify 51 genes differentially expressed between PEL cells and normal B cells as well as NHL, including AIDS-NHL. In the second study, 3 cases of freshly obtained AIDS-PEL mononuclear cells were expression profiled on the Affymetrix U133 GeneChip. In contrast, the intent of this project is to identify genes in PEL, whose expression is associated with long-term survival (≥ 2 years).

Currently, little is known about factors of prognostic importance in PEL. We hypothesize that there will be a sub-set of PEL clinical characteristics and differentially expressed genes in PEL cells that will be of prognostic value for this disease, when data from long-term and short-term survivors of the disease are compared.

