2.2 Study Design and Rationale

This is a retrospective analysis to determine the baseline characteristics, treatment patterns and gene expression associated with of long-term survival in HIV-seropositive and negative patients with PEL diagnosed on or after January 1, 1998, a time period during which use of HAART has been widespread in the United States. Due to the rare nature of this disease, data supporting optimal treatment strategies are limited. The AMC is interested in studying this disease because of the disproportional prevalence among people with HIV infection. Information gathered from this retrospective study might serve to initiate future prospective studies in the AMC.

In this study, patient, disease, and treatment information will be obtained from multiple centers within the AMC. Archived biopsy specimens of PEL will also be collected when available for genomics portion of the analysis. The AMC Operations and Data Management Center (AMC ODMC) will provide an electronic clinical research form (CRF) to all participating sites via the AMC AdvantageEDCSM Internet Data Entry System. Each participating AMC center will perform chart reviews after obtaining an Institutional Review Board (IRB) waiver or approval to conduct the study, as determined by the local IRB. All case data will be entered in AdvantageEDC in a de-identified manner, and protected health information (PHI) collected will be limited to information necessary to determine participant eligibility and to address the research questions. Data will be provided to [name]., at the AMC Statistical Center at the University of Arkansas for Medical Sciences for statistical analysis via secure electronic transfer. The data set will only be accessible by the registered investigators, [name] and [name], the statistician, [name], and the AMC ODMC for the purposes of data monitoring and analysis.

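### The only gene-expression test with named groups compares treatment responders with non-responders, while the primary genomic objective concerns survival of at least 2 years

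*Combined protocol and SAP*

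**What the plan says.** The aim is stated consistently. Section 1.2 sets the primary genomic objective as "Identify differentially expressed genes in PEL that are associated with long-term survival (≥ 2 years" or more. The hypothesis in section 1.1 expects predictive genes to emerge "when data from long-term and short-term survivors of the disease are compared". Section 2.1 gives the project's intent as to "identify genes in PEL, whose expression is associated with long-term survival (≥ 2 years" or more, and the design rationale in section 2.2 also refers to long-term survival.

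The analysis text in section 4.3.2.1 is different. After normalization the RNA-Seq data are "subjected to supervised analysis to identify genes differentially expressed between PEL treatment responders vs non-responders". The next sentence specifies how: a t-test with Westfall-Young permutation correction, at p < 0.05 and FDR < 0.05. The authors then expect that "fewer than 500 genes will be found to be differentially expressed between treatment responders and non-responders". Pathway tools will be used to "examine genes that are found to be differentially expressed between the sample groups".

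The section closes by stating that "RNA-Seq analyses, as described above will be performed on 20 PEL specimens, 10 of which are from long-term survivors and 10 from non-long-term survivors". The sentence after that concerns only the quality and adequacy of the resulting data.

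Section 5.1.1 adds DESeq, GeneSpring and Bioconductor, but does not say which sample groups are compared. Sections 4.3.2.2 and 4.3.2.3 describe the GeneChip assay and when it replaces RNA-Seq, and name no comparison.

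**The concern.** Response to treatment and survival at 2 years are different outcomes, and the protocol records them as separate items (section 3.1). A patient may respond and die before 2 years, so the two groupings need not contain the same people. A gene list from the responder comparison describes treatment response and is not an answer to the primary genomic objective.

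Two further consequences follow. I found no definition of responder for this analysis, so the written grouping could not be reproduced. And if the text and the objective disagree, the choice of comparison stays open until after the expression data have been seen.

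**Working it through.** The plan gives no figure to reproduce here: there is no power calculation, effect size or response rate for the expression analysis. The check is a comparison of every section that mentions differential expression, a test, or outcome groups.

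| Section | Groups named | Test named |
|---|---|---|
| 1.1, 1.2, 2.1, 2.2 | Survival groups or long-term survival | None |
| 4.3.2.1, supervised analysis | Responders vs non-responders | t-test, Westfall-Young |
| 4.3.2.1, expected yield | Responders vs non-responders | Same analysis |
| 4.3.2.1, the 20 specimens | 10 long-term, 10 non-long-term survivors | None of its own; refers back |
| 4.3.2.2, 4.3.2.3 (GeneChip) | None | None for a group comparison |
| 5.1.1, expression | Sample groups, not defined | DESeq; GeneSpring and Bioconductor algorithms |
| 5.1.1, survival | Treatment groups, categorical baseline variables | Kaplan-Meier, Cox |

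1. Two analysis statements name the groups whose expression is compared. Both use response and neither uses survival. They are one contrast repeated within a paragraph, so the count shows consistency and is not independent evidence.
2. The sentence on the 20 specimens refers back to analyses already described. The only group comparison described there is responders against non-responders, so the reference does not supply a survival test.
3. The Kaplan-Meier and Cox methods in section 5.1.1 are not applied to gene expression.
4. Two-year survival status is minimum data for every genomics participant (section 3.1). Response is not in that list and is only highly desirable for them (section 4.2.1.3). Participants may enrol in the genomic portion alone, so some could lack the written grouping variable. Their number is unknown, and section 5.2 expects clinical data on all 80. This is a lesser point.

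**Illustration of direction only, with assumed response rates.** Let the long-term share be p = 0.5 (10 + 10), with response probability a in long-term survivors and b in the others. Take a = 0.9 and b = 0.5.

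- Responders: 0.5 × 0.9 + 0.5 × 0.5 = 0.45 + 0.25 = 0.70. Non-responders: 0.5 × 0.1 + 0.5 × 0.5 = 0.05 + 0.25 = 0.30. Of 20 specimens that is 14 against 6 instead of 10 against 10.
- Gene that differs by d between survival groups only: the responder difference is d × (0.45/0.70 − 0.05/0.30) = d × (0.643 − 0.167) = 0.48d, against a survival difference of d.
- Gene that differs by d between response groups only: the responder difference is d and the survival difference is d × (0.9 − 0.5) = 0.4d, a ratio of 1/0.4 = 2.5.

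| Assumed a / b | Ratio, survival-only gene | Ratio, response-only gene |
|---|---|---|
| 0.8 / 0.5 | 0.33 | 3.3 |
| 0.9 / 0.5 | 0.48 | 2.5 |
| 1.0 / 0.1 | 0.91 | 1.1 |

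The ratio is the responder difference divided by the survival difference. The written test can understate survival genes and overstate response genes; the two contrasts come close only when response nearly coincides with survival group.

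**The case against.** The strongest reply is that the survival comparison is there by implication. The supervised test belongs to the general approach in section 4.3.2.1, and the closing sentence applies that approach to 10 long-term and 10 non-long-term survivors, so one fair reading applies the test to those groups. Section 5.1.1 mentions at least 10 known long-term survivors just before the differential-expression analysis and speaks of prognostic significance. On this view the responder wording is a slip.

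That supports the authors' probable intent, but it does not repair the text. The responder groups are written twice, and a reader must override them to reach the objective. Section 5.1.1 never says that the long-term survivors form one side of a comparison.

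It can also be said that this is a retrospective, exploratory case series and that no data are lost, since survival status is always collected. Both are true. They make the correction easy, but the mismatch still affects one of two primary objectives.

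The illustrative ratios rest on rates with no basis in the documents, and nothing in the conclusion depends on them. It is also right that substituting survival groups in the sentence on fewer than 500 genes would move an expectation stated only for response, so that figure needs its own confirmation. Finally, the t-test in section 4.3.2.1 and DESeq in section 5.1.1 are different methods for the same data; naming the contrast does not settle which is primary, and that is a separate question.

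**Conclusion.** The concern holds. The text is wrong as written, and this is more than missing detail: the only expression test with named groups is attached to treatment response, and no section attaches a test to the survival groups of the primary genomic objective. No numerical size can be given, and the direction of any distortion is open. The conclusion rests on the wording alone and assumes nothing about response rates or the number of genomics-only participants. It should be corrected before the expression data are analysed.

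**What to change.** 1. In section 4.3.2.1, replace the responder and non-responder groups with long-term (≥ 2 years) versus non-long-term survivors, in both the supervised-analysis sentence and the expected-yield sentence. Keep the expectation of fewer than 500 genes only if the authors confirm that it applies to the survival contrast; otherwise delete it.
2. In section 5.1.1, define the sample groups in the same way.
3. In section 4.3.2.2, add a sentence that the GeneChip fallback uses the same contrast.
4. If a responder comparison is still wanted, keep it as a labelled secondary or exploratory analysis in participants with a recorded response, with responder defined.

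The cost is a text amendment: two phrases in section 4.3.2.1, one definition in section 5.1.1 and one sentence in section 4.3.2.2, plus the optional responder text. No new participants, specimens or data items are needed for the primary contrast, because 2-year survival status is already mandatory for the genomic portion.

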3.1 Eligibility Criteria

Patients diagnosed with primary effusion lymphoma (HIV seropositive or negative) on or after January 1, 1998 on whom survival status at 2 years post PEL diagnosis is available.

Participants may be enrolled to *either or both* the clinical or genomic portions of the study.

The minimum data required to be able to include a participant for analysis of **clinical prognostic factors** are:

- a. HIV status, and for HIV-positive participants, include CD4 count, HIV viral load within one year prior PEL diagnosis (or within 3 months after PEL diagnosis)
- b. Age at PEL diagnosis
- c. Gender
- d. Stage at PEL diagnosis
- e. Treatment of PEL
- f. Response to PEL treatment
- g. Survival status at 2 years post diagnosis
- h. Pathology slides (or paraffin block) for central review
- i. Year of PEL diagnosis

The minimum data required to be able to include a participant for analysis of **genomic prognostic factors** are:

- a. Availability of a pathologic specimen of PEL that will be submitted for genomic analysis
- b. Survival status at 2 years post diagnosis

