4.2 Study Plan

- 4.2.1 Data, Documents, Records, or Specimen Identification:
 - 4.2.1.1 The following data will be collected for participants enrolled into the clinical portion of the study:
 - HIV status, and for HIV-positive participants, include CD4 count, HIV viral load within one year prior PEL diagnosis (or within 3 months after PEL diagnosis)
 - Age at PEL diagnosis
 - Gender
 - Stage at PEL diagnosis
 - Treatment of PEL
 - Best response to PEL treatment
 - Survival status at 2 years post diagnosis
 - Pathology slides for central review (See Appendix II for specimen preparation and shipping)
 - Year of PEL diagnosis
 - 4.2.1.2 The following will be collected for participants enrolled into the genomics portion of the study:
 - Pathology slides for central review (if unavailable, paraffin block may be submitted)
 - Pathologic specimen that will be submitted for genomic analysis:
 - Frozen specimens, formalin-fixed and paraffin-embedded (FFPE) demonstrating PEL including cytospins as well as any mass/nodal biopsies are acceptable (See Appendix II for specimen preparation and shipping)
 - Survival status at 2 years post diagnosis
 - 4.2.1.3 The following is a list of additional data that is highly desirable for inclusion whenever available for participants enrolled in either the clinical and/or genomics portion of the study:
 - Race and ethnicity
 - For participants with HIV: HIV treatment history (which HAART drugs has participant received prior to PEL diagnosis, after PEL diagnosis), baseline HIV characteristics (i.e., CD4 count and HIV viral load closest

to time of PEL diagnosis, history of opportunistic infections)

- Presence or history of other human herpesvirus-8 (HHV-8)-related diseases (i.e., Kaposi's sarcoma, Multicentric Castleman's Disease), and other malignancies)
- Lymphoma baseline disease characteristics (immunophenotype, Epstein-Barr virus (EBV) and Kaposi sarcoma herpes virus (KSHV) status, sites of extranodal involvement), and either IPI or data required for calculation of International Prognostic Index (IPI)
- Lymphoma treatment: type, number of treatment regimens, use of therapeutic effusion drainage
- Best response to PEL treatment, best response duration
- Survival status at time of enrollment and duration of survival in months from PEL diagnosis

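### The primary RNA-Seq analysis is written as a treatment-response contrast although the objective is 2-year survival, and Sections 4.3.2.1 and 5.1.1 name different tests with no single error rate.

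*Combined protocol and SAP*

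**What the plan says.** The primary genomic objective (Section 1.2) is to "Identify differentially expressed genes in PEL that are associated with long-term survival" of at least 2 years. The hypothesis (Section 1.1) likewise compares long-term with short-term survivors.

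Section 4.3.2.1 describes the supervised RNA-Seq analysis as a search for "genes differentially expressed between PEL treatment responders vs non-responders". It repeats that contrast in its forecast that "fewer than 500 genes will be found to be differentially expressed between treatment responders and non-responders". Its last paragraph then applies the analyses to 20 specimens, "10 of which are from long-term survivors and 10 from non-long-term survivors".

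The same section derives gene expression by summing FPKM values. It says the analysis will be "performed by means of t-test with multi-testing correction (Westfall & Young Permutation method"), and adds thresholds of p below 0.05 and FDR below 0.05.

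Section 5.1.1 says the RNA-Seq data will be analysed with DESeq. It refers only to unnamed sample groups and gives no error rate.

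For the genomic portion, Section 3.1 requires only survival status at 2 years and "Availability of a pathologic specimen of PEL that will be submitted for genomic analysis". Section 4.2.1.3 puts "Best response to PEL treatment, best response duration" among "additional data that is highly desirable for inclusion whenever available for participants enrolled in either the clinical and/or genomics portion of the study".

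**The concern.** The gene list is the result for one of the two primary objectives, and two parts of its definition conflict.

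**Contrast.** The only sentences that name the groups to be compared name response, not survival. An analyst who follows them reports genes linked to response. If expression follows survival, every patient who responded but died before 2 years is placed in the wrong group and dilutes the survival signal. The analysis may also lack data: response is not required for participants enrolled only in the genomic portion, and no section defines a responder.

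**Test and error rate.** A t-test on FPKM-based expression and DESeq differ in both model and input. Westfall-Young controls family-wise error, yet the threshold beside it is labelled FDR, and no FDR procedure is named. At least three rules could be defended: a family-wise t-test, an FDR t-test, or DESeq at some level. The choice among them could be made after the data are seen.

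**Working it through.** The documents contain no power calculation, effect size or number of genes tested for the genomic comparison, so there is no plan figure to reproduce. The contradictions follow from reading the sections together. The arithmetic only shows how much they matter.

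**1. The sections side by side**

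| Item | 4.3.2.1 | Elsewhere |
|---|---|---|
| Groups | Responders v non-responders (twice); then 10 v 10 by survival | Survival of at least 2 years (1.1, 1.2); unnamed sample groups (5.1.1) |
| Test | t-test | DESeq (5.1.1) |
| Input | Summed FPKM, normalized | Not stated in 5.1.1; DESeq models counts |
| Error rate | Westfall-Young, with p and FDR both below 0.05 | None in 5.1.1 |

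**2. Inputs**

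- From the documents: 10 v 10 specimens (4.3.2.1); a genomic minimum of 20 (3.3.1); up to 80 specimens profiled (5.1.1); long-term survivors 15-25% (5.2) or 25-40% (4.3.1), so 12, 20 or 32 of 80.
- Assumed: 20,000 genes, 500 truly linked to survival, normal data, and differences of 1, 1.5 or 2 SD. FDR control is by Benjamini-Hochberg (BH) at 5%.

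**3. Wrong contrast.** Suppose expression follows survival only, all 10 long-term survivors respond, and x of the 10 others also respond. The groups become (10 + x) v (10 - x). The mean difference shrinks to 10/(10 + x) of its value: 0.91, 0.83 and 0.77 for x = 1, 2 and 3. The variance in the responder group also rises, because it is now a mixture. True survival genes found (t-test, BH 5%, average of 30 simulated data sets):

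| x | 2 SD | 1.5 SD |
|---|---|---|
| 0 | 342 | 89 |
| 1 | 152 | 15 |
| 2 | 26 | 1.5 |
| 3 | 1 | 0.3 |

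Independent reruns at 2 SD gave about 15 to 26 for x = 2.

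With 80 specimens, 20 of them from long-term survivors who all respond:

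| Non-long-term responders | 2 SD | 1.5 SD | 1 SD |
|---|---|---|---|
| 0 of 60 | not tabulated | 494 | 331 |
| 6 of 60 | 497-498 | 437-446 | 139 |
| 18 of 60 | 350 | 132 | 3 |

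**4. Error rate, correct contrast.** At 10 v 10 and 2 SD a noncentral-t check is enough. The family-wise cut-off, using Bonferroni as a stand-in, is 0.05/20,000 = 2.5e-6. Power per gene there is 0.07, and 500 x 0.07 = 35 genes. With 360 genes declared, the BH cut-off is 0.05 x 360/20,000 = 0.0009. Power there is 0.68, and 500 x 0.68 = 340 genes. Simulation with Westfall-Young permutation agrees:

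| Setting | Westfall-Young | BH 5% | Ratio |
|---|---|---|---|
| 10 v 10, 2 SD | 35.9 | 341.2 | 9.5 |
| 10 v 10, 1.5 SD | 6.2 | 95.3 | 15.4 |
| 10 v 10, 2 SD, only 100 true genes | 7.2 | 36.2 | 5.0 |
| 10 v 10, 1.5 SD, only 100 true genes | 1.4 | 3.8 | 2.7 |
| 12 v 68, 1 SD | 24.4 | 158.5 | 6.5 |
| 20 v 60, 1 SD | 72.6 | 330.7 | 4.6 |
| 32 v 48, 1 SD | 136.8 | 418.8 | 3.1 |
| 20 v 60, 1.5 SD | 385 | 494 | 1.3 |

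Correlation between genes (blocks of 50, correlation 0.5) changes the first row little: 37.1 v 342.8. In that first row BH also lists 18.8 false genes, and 18.8/(341.2 + 18.8) = 5.2%.

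**The case against.** **Survival is plainly meant.** The hypothesis, the objective, the genomic eligibility rule and the specimen selection all say so. A reader might infer that the investigators really intend to study response, and the documents do not support that. This makes the contrast an error to correct rather than a rival objective. It does not remove the error: the responder wording appears twice, and 5.1.1 does not override it.

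**An error rate is stated.** A reader might infer that none is prespecified, and that goes too far. Section 4.3.2.1 gives thresholds and cites a procedure. Family-wise control at 5% also keeps FDR at or below 5%, and the p and FDR limits may be two separate thresholds. What remains is an ambiguous label, no named FDR procedure, and silence in 5.1.1.

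**The severe losses are 10 v 10 results.** This stands. A reader might infer that a few discordant patients would remove most survival genes at any sample size, or that the error-rate choice always changes the list about tenfold. Section 5.1.1 allows up to 80 specimens, and the 20 may be read as a first stage for quality assessment. At 80, 6 discordant of 60 leave most genes in place at 1.5-2 SD.

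**DESeq at 5% FDR is partly a preference.** This also stands. Family-wise control is legitimate, and DESeq itself was not run in these checks. The documents support naming one method, not a particular one.

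**Conclusion.** The point holds, and it should be corrected before analysis. As written, 4.3.2.1 directs the primary genomic analysis at response rather than survival, and 4.3.2.1 and 5.1.1 disagree on test, input and error rate with no rule of precedence. These conclusions rest on the text alone, and the contrast is the weightier part.

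The size depends on assumed effects and on how many specimens are analysed. At 10 v 10 and 2 SD, two discordant patients cut the true genes found from about 340 to about 15-26, and Westfall-Young finds about 36 against 341 at 5% FDR. With 80 specimens (20 v 60) and 6 of 60 discordant, about 437-498 of the 500 true genes are still found at 1.5-2 SD. The loss is large only with weaker effects (about 140 against 330 at 1 SD) or greater discordance. The error-rate gap at 80 runs from about 1.3-fold (1.5 SD, 20 v 60) to 6.5-fold (1 SD, 12 v 68) in the settings examined. All these figures assume 20,000 genes, 500 of them true, and normal data; the contrast figures also assume that expression follows survival only and that every long-term survivor responds.

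**What to change.** - In 4.3.2.1, replace the responder contrast in both places with long-term (at least 2 years) v non-long-term survivors. Alternatively, label the responder contrast secondary, define a responder, and name survival as the primary contrast.
- In 4.3.2.1 and 5.1.1, state in identical words one primary test, its input data, and one error rate with its level. One example is DESeq on gene-level counts at 5% FDR.
- If Westfall-Young is kept, call it family-wise error and drop the FDR label from it.

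The cost is wording in two sections; specimens and assays are unchanged. Choosing 5% FDR has a price: about 5% of listed genes are expected to be false (about 19 of 360 in the 10 v 10, 2 SD case), against almost none under family-wise control. Choosing family-wise control has the opposite price, a shorter list. DESeq's realised error rate at these sample sizes was not checked here.
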